## 10 IMMUNOLOGY

The results for the anti-drug (bimekizumab) antibody (ADA) measurements will be listed by PS0016 randomized treatment group and timepoint based on the SS, including the screening assay, confirmatory assay and titer (if applicable).

A cut point will be determined by the bioanalytical laboratory that will be used to determine the status of ADA as above the cut point (ACP) or below the cut point (BCP). For any ADA levels that are ACP, a further confirmatory assay will be performed, the results of which will be determined as either 'confirmed positive' (CP) or 'not confirmed positive' (NCP). For samples that are CP, a further titer assay will be performed and the ADA titer will be reported.

The following definitions will be applied 2 ways: firstly including the PS0018 SFU visit, and then excluding the PS0018 SFU visit:

- An ADA status of positive will be concluded for any subject with an ADA level that is ACP and CP at any timepoint (PS0016 Baseline, Week 4 and Week 8, and all PS0018 visits)
- An ADA status of negative will be concluded for any subject with an ADA level that is either BCP or ACP and NCP at any timepoint (PS0016 Baseline, Week 4 and Week 8, and all PS0018 visits)
- A subject will be classified as having ADA positivity at PS0016 Baseline if the PS0016 Day 1, predose result is ACP and CP
- A subject will be classified as having treatment-induced ADA positivity when meeting one of the following criteria:
  - The PS0016 Baseline result is either BCP or ACP and NCP, and at least one PS0018 timepoint is ACP and CP
  - The PS0016 Baseline result is positive (ACP and CP) and at least one PS0018 measurement shows a pre-defined fold increase in titer from the Baseline value (the fold increase from PS0016 Baseline required to meet this criteria will be defined with the development of the assay and will be included in the TFLs)
- A subject will be classified as overall positive if at least one PS0018 measurement is ACP and CP (this includes subjects who have negative results at Baseline)
- A subject will be classified as overall negative if at all PS0018 visits the ADA status is negative (this includes subjects who have positive [ACP and CP] results at Baseline)

All listings, summaries and figures will include the PS0016 visits Baseline, Week 4 and Week 8 and all PS0018 visits.

The ADA status (positive/negative) will be summarized as a categorical endpoint (number and percentage of subjects) by PS0016 randomized treatment group for all timepoints and overall, based on the SS.

In addition, the first occurrence of treatment-induced ADA positivity (based on the definitions above) will be summarized (number and percentage of subjects) by PS0016 randomized treatment group at the visits PS0016 Baseline and Week 4 and Week 8 of PS0016 and additionally at each PS0018 visit, based on the SS. This tabulation will count the number of subjects at each PS0018 visit who fulfill at least one of the above defined criteria for treatment-induced positivity; subjects will be counted in the numerator based on the earliest visit at which one of these criteria is fulfilled. At other visits, subjects will be counted in the denominator (assuming a measurement is available). For all tabulations, percentages will be based on the number of observations at each visit.

A separate listing will be presented (based on the SS) showing the bimekizumab concentrations and ADA measurements in the same output in adjacent columns. The listing will include the bimekizumab concentration, ADA status (ACP or BCP) and confirmatory assay results if applicable (NCP or CP), together with the titer for results that are CP. In addition, the time since the previous administration of study medication will be reported (in days).

Finally, individual subject plots will be presented displaying the PASI total score, ADA titer and bimekizumab concentrations overlaid on the same figure. The figure will also show the timing and dose of each administration of bimekizumab received during the study. The ADA data will be plotted using a semi-logarithmic scale.

The rules for handling values that are BLQ in the bimekizumab concentration data are described in [Section 4.2.3](#). For the ADA data, any negative results for which there are no titers available at a specific visit will be substituted with 0.001 for the purpose of the figure.

## 11 SAFETY ANALYSES

All analysis of safety variables will be performed using the SS, unless otherwise stated. Changes from Baseline for all safety variables are changes from PS0016 Baseline.

### 11.1 Extent of exposure

#### 11.1.1 Drug administration

All drug administration details (including date, time of injection, location, side of body and volume delivered) will be listed by subject and visit. The study medication will be given as 1 or 2 sc injections depending on dose, at each planned dosing visit (PS0018 Week 0, Weeks 4, 8, 12, 16, 20, 24, 28, 32, 40 and Week 44).

The duration of exposure (in days) will be calculated as:

$$\text{Date of last dose in PS0018} - \text{Date of first dose in PS0018} + 28 \quad [10]$$

Should the date of the last dose plus 28 days equate to a date that is beyond the Week 48 visit date then the exposure will be calculated as:

$$\text{Week 48 visit date} - \text{Date of first dose in PS0018} + 1 \quad [11]$$

For subjects who have died the exposure will be as follows:

$$\text{Date of death} - \text{Date of first dose in PS0018} + 1 \quad [12]$$

For subjects who switched dose during PS0018, the duration of dose within each dose interval (except the last dose interval) will be calculated as:

$$\text{Date of last dose in PS0018} - \text{Date of first dose in PS0018} + 1 \quad [13]$$

The dose taken in the last dose interval will be calculated as:

$$\text{Date of last dose in PS0018} - \text{Date of first dose in PS0018} + 28 \quad [14]$$

In this case duration of exposure will be calculated as the sum of the dose intervals for bimekizumab 160mg Q4W and 320mg Q4W, respectively.

Extent of exposure in PS0018 will be summarized using descriptive statistics and presented by bimekizumab 160mg Q4W, 320mg Q4W, respectively and All bimekizumab.

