#### 3.2.1.2 Study periods

For each subject, the study duration is estimated to be up to a maximum of 64 weeks:

- Open-Label Treatment Period: 48 weeks
- SFU Visit: 20 weeks after the last dose of study medication scheduled at Week 44

The end of the study is defined as the date of the last visit of the last subject in the study.

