#### 11.1.2 Subject time at risk

The subject time at risk represents the time a subject was at risk for having an AE and will be used to calculate the exposure adjusted incidence rate (EAIR) and exposure adjusted event rate (EAER) as described in [Section 11.2.2](#).

The subject time at risk (days) will be calculated as follows:

$$\text{Time at risk} = (\text{Date of Last PS0018 IMP} - \text{Date of First PS0018 IMP}) + 140 \quad [15]$$

This includes the duration of the SFU Period.

For subjects who switch dose during PS0018, time at risk will be derived in each dose interval and calculated as per equation [13] above, and equation [15] will be applied for the dose in the final dose interval.

In cases where the last clinical contact or last visit occurs prior to completion of the SFU period, the subject time at risk is calculated as follows:

$$\text{Time at Risk} = (\text{Date of Last Contact} - \text{Date of First PS0018 IMP}) + 1 \quad [16]$$

This will apply for the following:

- For subjects that discontinue prematurely (ie, and no SFU data are available), the date of final contact refers to the date of the latest contact with the subject during the study PS0018 after which no further information or data are available. This will be reported on the study termination page of the electronic Case Report Form (eCRF).
- For subjects that have died during the study the date of last contact refers to the date of death

The sum of these exposure days at risk across subjects in the relevant PS0018 dose group is converted to years for the EAIR and EAER calculations described in [Section 11.2.2](#).

Subject-years at risk is defined as the subject time (in days) at risk divided by 365.25. The days at risk and subject years at risk will be listed and summed by PS0018 dose at onset, together with the drug administration information ([Section 11.1.1](#)).

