## 11.2 Adverse events

### 11.2.1 Definitions and classification of adverse events

All AEs will be recorded in the CRF from informed consent until study completion or termination.

Adverse events will be coded according to MedDRA® version 19.0. Treatment-emergent adverse events (TEAEs) will be defined as events that have a start date on or after the first administration of study treatment in PS0018 until the last received dose of study medication +140 days (which covers the 20-week SFU Period). Adverse events occurring after this date will not be classified as TEAEs and will therefore be excluded from the summary tables. TEAEs will be categorized according to the PS0018 dose at onset, ie, the last dose being received at the time of onset of the event. If a TEAE occurs on the same day as a change in dosage and it cannot be clearly established whether or not the TEAE started before or after dosing, because for example the time of the AE is missing, then the TEAE will be attributed to the treatment dose that the subject has just completed, unless the adverse event is related to the injection (ie higher level term (HLT) of “injection site reactions”) or an anaphylactic reaction ([Section 14.3.7.1](#)), in which case the TEAE will be assigned to the treatment dose administered on that day. Tables will include columns for BKZ 160mg Q4W, BKZ 320mg Q4W, and All BKZ.

Any adverse events considered ongoing from PS0016 which do not worsen in severity during PS0018, or starting prior to first PS0018 dose will not be considered treatment emergent in PS0018 and will be tabulated separately.

In order to evaluate if there is any difference in the TEAE profile of subjects who have dose adjustments, additional summaries will be generated based on Dose adjustment described in [Section 3.6](#) for select tables as given in [Section 11.2.3](#).

Where dates are missing or partially missing, AEs will be assumed to be treatment-emergent, unless there is clear evidence to suggest that the AE started prior to PS0018 dosing. Handling of missing dates/times for classification of AEs as TEAEs is described in [Section 4.2.4](#).

All AEs will be coded and categorized by intensity (mild/moderate/severe) and relationship to study medication (related/not related).

In summaries including relationship to study medication, the following relationship categories will be included:

- Related
- Not related

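### SAP 11.1.1, equation [12]: duration of exposure runs to the date of death without a cap, so a death 28 or more days after the last dose counts follow-up time as treatment exposure

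*SAP*

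**What the plan says.** SAP 11.1.1 (Drug administration) gives these rules for duration of exposure in days:

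- Equation [10], the general rule: last dose minus first dose, plus 28.
- Equation [11], which applies as follows: "Should the date of the last dose plus 28 days equate to a date that is beyond the Week 48 visit date". Exposure then stops at that visit: Week 48 visit minus first dose, plus 1.
- Equation [12], introduced by "For subjects who have died the exposure will be as follows": date of death minus first dose, plus 1.
- Equations [13] and [14], for subjects who switched dose: each earlier interval runs from its first to its last dose, plus 1, and the last interval ends with plus 28.

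The result is summarised descriptively for 160mg Q4W, 320mg Q4W and all bimekizumab.

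Follow-up has its own measure. SAP 11.1.2 (Subject time at risk) adds 140 days to the dosing period ([15]). If contact ends before the follow-up period is complete, it runs to last contact ([16]), and "For subjects that have died during the study the date of last contact refers to the date of death". SAP 11.2.1 counts adverse events as treatment-emergent "until the last received dose of study medication +140 days (which covers the 20-week SFU Period").

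**The concern.** No non-fatal route lets exposure run beyond the 28-day dosing interval after the last dose. Equation [11] can only shorten it, and the last interval of a dose switcher also ends at 28 days. Equation [12] is the exception. It applies to every death, whenever it occurs, and has the same form as [16] applied to a death. That form suits time at risk, which is meant to include the 20-week follow-up. It does not suit treatment duration, which elsewhere stops at 28 days. SAP 6.5.2 likewise closes the treatment period for concomitant medication 28 days after the last dose.

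The SAP also sets no order between the rules. A completer who dies in follow-up can meet the conditions of both [11] and [12]. A dose switcher who dies falls under [12] and [13]/[14], and nothing says how the time to death is divided between the two dose columns.

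What is at stake is the exposure table: its mean, its maximum and the value for the subject who died. Two subjects with identical dosing would be reported with different treatment durations only because one died after treatment ended.

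**Working it through.** **Inputs**

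- Equations [10] to [14]: SAP 11.1.1. Equations [15] and [16]: SAP 11.1.2.
- Completer's last dose: Week 44, which is 44 × 7 = 308 days after the first dose (SAP 3.2.1.2: "SFU Visit: 20 weeks after the last dose of study medication scheduled at Week 44").
- Follow-up: 140 days after the last dose. The follow-up visit window of -3/+7 days (Protocol 8) allows day 147.
- Up to 45 subjects (SAP 2.4).

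**Reproducing the plan's figures.** Equation [10] for a full course gives 308 + 28 = 336 days = 48 weeks, the stated treatment period. The last dose plus follow-up gives 44 + 20 = 64 weeks, the stated maximum study duration. So [10] behaves as intended.

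**Difference between [12] and [10].** Let d be the days from first to last dose and k the days from last dose to death.

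- [10] = d + 28
- [12] = d + k + 1
- [12] - [10] = k - 27, whatever the value of d

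| k (days from last dose to death) | [12] - [10] (days) |
|---|---|
| 10 | -17 |
| 27 | 0 |
| 28 | +1 |
| 60 | +33 |
| 140 | +113 |
| 147 | +120 |

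Up to day 26 after the last dose, [12] shortens exposure, as it should. The rules agree at day 27, and the excess starts at day 28. The formula sets no upper limit.

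**Death at day 140, by last dose received**

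| Last dose | d | [12] | [10] | Excess relative to [10] |
|---|---|---|---|---|
| Single dose (Week 0) | 0 | 141 | 28 | 404% |
| Week 8 | 56 | 197 | 84 | 135% |
| Week 12 | 84 | 225 | 112 | 101% |
| Week 44 | 308 | 449 | 336 | 33.6% |

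**Effect on the summary.** Assume 45 subjects with full courses and one death at day 140. Mean exposure rises by 113/45 = 2.5 days, and total exposure by 113/(45 × 336) = 0.75%. The maximum would read 449 days against a planned 336.

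**Effect on the rates.** SAP 11.2.2 takes the denominators of the exposure-adjusted incidence rate (EAIR) and event rate (EAER) from time at risk in 11.1.2, or, for the EAIR in subjects with the event, from the time to its onset. None uses [10] to [14] as a duration of exposure. The one shared formula is [13], borrowed for earlier dose intervals, and it is not at issue. The change to these rates from [12] is zero.

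**The case against.** Four arguments carry weight.

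- **The effect is very small.** It needs a death at least 28 days after the last dose among at most 45 subjects. Even then the mean moves by 2.5 days in the illustration above. This stands and sets the weight of the point.
- **The dosing period is visible elsewhere.** SAP 5.1 lists days on study medication as last dose minus first dose plus 1, with first and last dose dates, and 11.1.1 lists every administration. A reader could spot an implausible value. This reduces the harm but does not correct the table.
- **Equation [12] may be a truncation rule, loosely worded.** It follows [11], which only shortens exposure, and Protocol 14.2.1 censors exposure at risk at death. That may well be the intent. As written, however, [12] extends as well as truncates, and the protocol sentence concerns time at risk, not treatment duration.
- **Drug remains in the body after day 28.** Protocol 2.2.1 reports a median half-life of about 28 days, and Protocol 6.1 equates 20 weeks with 5 half-lives. It would therefore be wrong to call the added time drug-free. The valid description is time beyond the 28-day dosing interval. The half-life does not justify [12] either, because a survivor with the same last dose is still stopped at 28 days.

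A reader might also infer that the primary safety analysis is distorted, since its variable is exposure-adjusted. The documents do not support that: the EAIR and EAER rest on time at risk, and for that quantity both the protocol and the SAP intend death to be the end date.

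**Conclusion.** The rule is wrong as written for any death 28 or more days after the last dose, and no other section caps it. The overstatement is k - 27 days for a death k days after the last dose, measured against [10]: 113 days at day 140 and 120 at the end of the follow-up visit window. Where [11] has already shortened exposure, the gap is slightly larger.

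The consequence is confined to the descriptive extent-of-exposure summary: its mean, its maximum and that subject's value. The primary EAIR and the EAER are unaffected. That zero or one subject would be affected is an assumption based on the small sample; the documents give no expected death rate. The 2.5-day shift in the mean further assumes 45 full courses and a death at day 140. This is a minor correction, worth making because it is free and because it avoids deciding how to handle a fatal case during programming.

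**What to change.** In SAP 11.1.1, for subjects who die, define duration of exposure as the smallest applicable value of [10], [11] and [12], using [11] only if a Week 48 visit took place. Equivalently:

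min(date of death, last dose + 27 days, Week 48 visit date if there is one) - first dose + 1

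The end date must be last dose + 27, not + 28. In a formula that ends with plus 1, last dose + 28 would give d + 29, still one day more than [10].

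For a subject who switched dose and then died, apply the same end date to the last dose interval in place of [14], counting from the first dose of that interval. This also settles which dose column receives the time after the last dose.

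The cost is one or two lines in the SAP and the matching line of derivation code. Values for survivors, and for subjects who die on or before the capped end date, do not change. Leave SAP 11.1.2 as it is.

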#### 11.1.2 Subject time at risk

The subject time at risk represents the time a subject was at risk for having an AE and will be used to calculate the exposure adjusted incidence rate (EAIR) and exposure adjusted event rate (EAER) as described in [Section 11.2.2](#).

The subject time at risk (days) will be calculated as follows:

$$\text{Time at risk} = (\text{Date of Last PS0018 IMP} - \text{Date of First PS0018 IMP}) + 140 \quad [15]$$

This includes the duration of the SFU Period.

For subjects who switch dose during PS0018, time at risk will be derived in each dose interval and calculated as per equation [13] above, and equation [15] will be applied for the dose in the final dose interval.

In cases where the last clinical contact or last visit occurs prior to completion of the SFU period, the subject time at risk is calculated as follows:

$$\text{Time at Risk} = (\text{Date of Last Contact} - \text{Date of First PS0018 IMP}) + 1 \quad [16]$$

This will apply for the following:

- For subjects that discontinue prematurely (ie, and no SFU data are available), the date of final contact refers to the date of the latest contact with the subject during the study PS0018 after which no further information or data are available. This will be reported on the study termination page of the electronic Case Report Form (eCRF).
- For subjects that have died during the study the date of last contact refers to the date of death

The sum of these exposure days at risk across subjects in the relevant PS0018 dose group is converted to years for the EAIR and EAER calculations described in [Section 11.2.2](#).

Subject-years at risk is defined as the subject time (in days) at risk divided by 365.25. The days at risk and subject years at risk will be listed and summed by PS0018 dose at onset, together with the drug administration information ([Section 11.1.1](#)).

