#### 2.1.2 Secondary objectives

Secondary objectives of the study are:

- To assess the safety and tolerability of increasing the dose of bimekizumab from 160mg every four weeks (Q4W) to 320mg Q4W for subjects with an inadequate response at Week 12
- To assess pharmacokinetics (PK) of bimekizumab
- To assess the immunogenicity of bimekizumab
- To assess the efficacy of open label bimekizumab 160mg Q4W administered over 48 weeks

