## 2.3 Study design and conduct

PS0018 is a multicenter, 48-week, open-label extension study to assess the long-term safety, tolerability, and efficacy of bimekizumab in eligible adult subjects with moderate to severe chronic plaque psoriasis who participated in PS0016.

During the Open-Label Treatment Period, subjects will attend study visits at the site Q4W for study assessments and administration of bimekizumab by study site staff through Week 48. Following completion or Withdrawal (WD) from the 48-week Open-Label Treatment Period, subjects will return for a Safety Follow-Up (SFU) Visit 20 weeks after their last dose of bimekizumab. Subjects withdrawing early from the study will also undergo the WD assessments and will enter the SFU Visit.

Bimekizumab will initially be administered at a dose of 160mg Q4W subcutaneously (sc) during the 48 week Open-Label Treatment Period. There will be an option to increase the dose to 320mg Q4W at the discretion of the Investigator if the subject's PASI reduction is  $\geq 50\%$  to  $< 75\%$  from the PS0016 Baseline at Week 12 or later in the PS0018 study. If the subject's disease is adequately controlled on the 320mg Q4W dose, they may return to 160mg Q4W at the discretion of the Investigator. The decision to return to 160mg Q4W dosing should be based upon treatment response, tolerability, and Investigator discretion, with the aim to use the dosing regimen that achieves the optimal benefit-risk for each subject. If a subject does not achieve a PASI50 at Week 12 or later during the PS0018 study based on change from PS0016 Baseline then they will be withdrawn from the study.

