## 2.4 Determination of sample size

Up to 45 subjects are anticipated to enroll in PS0018. This number is based on the fact that 45 subjects are planned to be randomized in the feeder study, PS0016. The calculations to reach that sample size are outlined in the PS0016 protocol. As the primary objective of the PS0018 study is to assess the long-term safety and tolerability of bimekizumab 160mg Q4W, the number of subjects anticipated is based on the number of subjects completing PS0016 and meeting eligibility requirements for PS0018.

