## 7 MEASUREMENTS OF TREATMENT COMPLIANCE

During the Open-Label treatment period of this study, study medication will be administered in the clinic and compliance will be determined at the visit by study personnel.

Due to the method of administration of the treatments, compliance will be examined in terms of completed number of injections. One dose of 160 mg requires one injection, one dose adjustment of 320 mg requires two injections. A dose reduction from 320 mg back down to 160 mg is allowed.

Treatment compliance will be calculated as:

$$\text{Overall compliance (\%)} = \frac{\text{total number of completed injections}}{\text{total number of expected injections}} \times 100 \quad [6]$$

where the total number of expected injections is derived relative to when the subject finishes treatment. If a subject discontinues early, then the number of expected completed injections is based on the date of early discontinuation relative to the dosing visits. The planned dose recorded at a given visit will indicate if one injection for bimekizumab 160 mg Q4W, or two injections for bimekizumab 320mg Q4W are expected to be given. If a subject completes treatment with no dose adjustment, 12 injections are expected (one each at Weeks 0, 4, 8, 12, etc. through to Week 44).

The calculated overall compliance will be listed by PS0016 randomized treatment group and subject, and summarized by PS0016 randomized treatment group, based on the SS. The summary will include both descriptive statistics for overall compliance (n, mean, SD, median, minimum and maximum) and the number and percentage of subjects based on the following classifications:

- Compliance  $\leq$ 80.0%
- Compliance  $>$ 80.0%

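### The 160mg and 320mg TEAE rates by dose at onset cover different study periods, so they can differ with no dose difference; the SAP plans no rate that separates period from dose

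*SAP*

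**What the plan says.** One secondary objective is: "To assess the safety and tolerability of increasing the dose of bimekizumab from 160mg every four weeks (Q4W) to 320mg Q4W" (SAP 2.1.2). All subjects begin on 160mg. An increase is possible for a PASI response of at least 50% but below 75%, "at Week 12 or later in the PS0018 study", and if the disease is controlled on 320mg "they may return to 160mg Q4W at the discretion of the Investigator" (SAP 2.3).

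Events are assigned to a dose column as follows: "TEAEs will be categorized according to the PS0018 dose at onset, ie, the last dose being received at the time of onset of the event" (SAP 11.2.1). The TEAE window runs to 140 days after the last dose. For subjects who change dose, SAP 11.1.2 gives each earlier interval its dosing days only, under equation [13]. For the last interval, "equation [15] will be applied for the dose in the final dose interval", and that equation carries the 140 days. Events and time in follow-up therefore both go to the last dose received.

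SAP 11.2.3 plans EAIR and EAER only in tables by PS0018 dose at onset: any TEAE, any TEAE by ADA status, and the adverse events of special monitoring. The dose-adjustment tables show incidence without exposure adjustment. No rate is planned for Week 12 onward, or for the on-treatment window alone.

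**The concern.** The dose columns stand side by side and will be read for the dose-increase objective, but they do not cover the same parts of the study. The 160mg column holds all of Weeks 0-12. The 320mg column holds none of it and, for a subject who finishes on 320mg, holds the whole tail.

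Event capture may differ between these periods. AEs are prompted at each visit (Protocol 9.1.2). Visits are every 4 weeks to Week 48, after which a completer has one scheduled visit, 20 weeks after the last dose (Protocol Table 5-1). Drug exposure is also declining by then, with a half-life of about 28 days (Protocol 2.2.1). If TEAEs are more frequent early, or captured less in follow-up, that period effect appears in the table as a dose effect. For subjects who stay on 320mg it makes 320mg look safer, and nothing else in the planned output would show why.

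**Working it through.** **Inputs from the documents.** Up to 45 subjects (SAP 2.4). Twelve dosing visits from Week 0 to Week 44 (SAP 7), so the last dose is 44 × 7 = 308 days after the first. The tail is 140 days (SAP 11.1.2). The SAP's exposure window ends 28 days after the last dose (SAP 11.1.1), which leaves 140 − 28 = 112 days, called follow-up below. The earliest increase is at Week 12, day 84.

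**Plan's own figure.** Equation [15] for a completer gives 308 + 140 = 448 days = 64 weeks. This matches the maximum study duration in SAP 3.2.1.2.

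**Assumptions, because the documents give no figures.** Ten of 45 subjects increase, all in the same week w. In the base case all complete and none returns to 160mg. Each dose interval is counted in full, so the result does not depend on how equations [13] and [15] are worded. The true TEAE rate is the same for both doses and differs only by period: e in Weeks 0-12, 1 later on treatment, f in follow-up.

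**Time in days**
- 160mg: 35 × 448 + 10 × 7w. Of this, 45 × 84 = 3,780 is early and 35 × 112 = 3,920 is follow-up.
- 320mg: 10 × (448 − 7w). Of this, 10 × 112 = 1,120 is follow-up and none is early.

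| Increase at | 160mg days | Early share of 160mg | Follow-up share of 160mg | 320mg days | Follow-up share of 320mg |
|---|---|---|---|---|---|
| Week 12 | 16,520 | 22.9% | 23.7% | 3,640 | 30.8% |
| Week 24 | 17,360 | 21.8% | 22.6% | 2,800 | 40.0% |
| Week 36 | 18,200 | 20.8% | 21.5% | 1,960 | 57.1% |

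For a single completing nonadjuster the follow-up share is 112/448 = 25%.

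**EAER ratio 320:160 with no dose difference**

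Ratio = [(T320 − F320(1 − f)) / T320] ÷ [(T160 − F160(1 − f) + 3,780(e − 1)) / T160], where T is time and F is follow-up time.

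Week 12, e = 1, f = 0.5: (3,640 − 560)/3,640 = 0.846; (16,520 − 1,960)/16,520 = 0.881; ratio 0.96. With e = 1.5 the 160mg term becomes (16,520 − 1,960 + 1,890)/16,520 = 0.996; ratio 0.85.

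| Increase at | Flat rate | f = 0.5 | e = 1.5, f = 0.5 |
|---|---|---|---|
| Week 12 | 1.00 | 0.96 | 0.85 |
| Week 24 | 1.00 | 0.90 | 0.80 |
| Week 36 | 1.00 | 0.80 | 0.72 |

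Milder values (e = 1.25, f = 0.75) give 0.925 for an increase at Week 12. With 5 or 15 adjusters instead of 10, the two right-hand columns span 0.71 to 0.96.

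**Where the follow-up imbalance goes away (increase at Week 12)**
- *Early withdrawal.* Fifteen of the 35 nonadjusters take their last dose at Week 8, so each has 56 + 140 = 196 days. 160mg time is 20 × 448 + 15 × 196 + 840 = 12,740, and 3,920/12,740 = 30.8%, the same as 320mg. With f = 0.5 alone the ratio is 1.00. With e = 1.5 as well it is still 0.85, because the Weeks 0-12 difference remains.
- *Return to 160mg.* Five of the 10 adjusters return at Week 28. 320mg follow-up is 560/(5 × 364 + 5 × 112) = 23.5%. For 160mg it is 40 × 112/(15,680 + 5 × 84 + 5 × 336) = 25.2%, so the order reverses. If all 10 return, the 320mg share is 0%, the 160mg share is 5,040/19,040 = 26.5%, and with e = 1.5 and f = 0.5 the ratio is 1.03.

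**Effect of a common window.** If both columns are cut to the Week 12 dose through last dose + 28 days, the ratio is 1.00 in every scenario, by construction. The 320mg time left is 10 × (308 − 84 + 28) = 2,520 days = 6.9 subject-years for an increase at Week 12, and 10 × 84 = 840 days = 2.3 subject-years at Week 36.

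**The case against.** The period rates are assumed. Weeks 0-12 are not first exposure, since both PS0016 arms had 320mg at Baseline and Week 4, and ongoing PS0016 events that do not worsen are not TEAEs. In follow-up, AEs are still recorded to study completion, the prompt asks about the time since the last visit, and unscheduled visits are allowed. The 0.80 and 0.72 need every adjuster to increase at Week 36, while the objective speaks of inadequate response at Week 12. The protocol prespecified the 140-day window for both events and time at risk. The tables are descriptive, no dose comparison is planned, and the AE listing shows dose at onset and days since the most recent dose. All of this stands. It limits the size of the problem and how much it matters, but does not make the columns comparable.

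Two stronger readings are tempting. The first is that 320mg always carries more follow-up time and so must look safer. The documents do not support it: return to 160mg is allowed, and SAP 4.2 expects many cases of missing data from treatment discontinuation as PASI50 failures are withdrawn. Either can equalize or reverse the shares. The second is that a period-restricted table would be a like-for-like dose comparison on which to base the dose-increase conclusion. It would not be, because 320mg goes only to subjects with a PASI response of 50% to below 75%, and those who increase at Week 12 have no 160mg time left in the window.

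**Conclusion.** The point holds in conditional form. That 320mg time excludes Weeks 0-12 follows from the design without exception. The larger follow-up share is certain only for subjects who finish on 320mg, compared with a completing nonadjuster (31% to 57% against 25%); the pooled imbalance depends on how many return to 160mg or withdraw early.

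If the TEAE rate is higher early, or captured less in follow-up, the EAER ratio falls below 1 with no dose difference. It is 0.96 or 0.85 for increases at Week 12 and 0.80 or 0.72 at Week 36, assuming that all complete and none returns. With a flat rate it is 1.00. These are EAER figures; no EAIR ratio was computed, because EAIR time stops at the first event. The days counted as follow-up are a period of declining exposure, not a drug-free one. The All BKZ column is not affected by the split between doses. Because the analysis is descriptive, this warrants a supportive table and a footnote, not a change to the primary table.

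**What to change.** Keep the planned table. Add one supportive table to SAP 11.2.3 giving EAIR and EAER by PS0018 dose for TEAEs with onset from the Week 12 dose to last dose + 28 days. Cut events, first-event time and time at risk all to that window, so that the clock no longer runs from the first PS0018 dose. Read this table beside the planned one for the dose-increase objective. Footnote that subjects on 320mg are selected partial responders, so a difference between columns is not a pure dose effect.

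The cost is SAP wording and one table, with no new data. The downside is fewer events and little 320mg time: about 6.9 subject-years with 10 adjusters at Week 12, and 2.3 at Week 36. Intervals will be wide.
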